### Study Identification

1. \* Select the Principal Investigator:

[name]

2. \* Study Title:

Do Intraoperative Periarthicular Injections Improve Postoperative Pain Control in Patients Receiving Duramorph? – A Prospective, Double-Blinded, Randomized Controlled Trial

3. \* Is this a student or trainee project in which activities will be carried out by that individual under your supervision (for example, dissertation or degree-required projects):

- Yes
- No

4. \* Please select the primary department or center that this study is being conducted under:

Orthopaedic Surgery

[Redacted text block]

7. \* Select one of the following that applies to the project (selection will branch to new pages):

Note: VCU IRB offers guidance for many types of studies, including secondary data analysis studies, internet research, registries, EFIC, HUD, and Emergency Use protocols.

See [https://research.vcu.edu/human\\_research/guidance.htm](https://research.vcu.edu/human_research/guidance.htm)

- Research Project or Clinical Investigation [most exempt, expedited, and full board research studies]
- Exception from Informed Consent (EFIC) for Planned Emergency Research
- Humanitarian Use of Device for Treatment or Diagnosis
- Humanitarian Use of Device for Clinical Investigation
- Emergency Use of Investigational Drug, Biologic or Device
- Treatment Use (Expanded Access to Investigational Product for Treatment Use)
- Center or Institute Administrative Grant Review
- Request for Not Human Subject Research Determination (i.e. request a letter confirming that IRB review is not required)

## Federal Regulations

1. \* Is this a FDA regulated study?

FDA regulated research includes all clinical investigations involving a test article and a human subject(s) that has been submitted for approval to the FDA or may be submitted in the future.

Check Yes if

- the study involves an IND/IDE, abbreviated IDE, IND/IDE exemption, HUD, expanded access, or is otherwise subject to 21 CFR 312.61,
- the study involves a test article being administered or dispensed to subjects NOT according to a clinician's medical judgment but rather, per the study protocol, OR
- the study does not involve a test article but intends to provide safety or efficacy data to the FDA.

Yes  No

2. \* Indicate the FDA regulated product(s) this study involves:

- Drug
- Medical Device
- Biologic
- Dietary Supplement
- Food/Food Additive
- Color Additive
- Electronic Products for Human Use (radiation producing)
- Other

[REDACTED]

[REDACTED]

HM20004125 [name]  
Do Intraoperative Periarthicular Injections Improve Postoperative Pain Control in Patients Receiving Duramorph? A Prospective, Double  
Blinded, Randomized Controlled Trial

## Study Population

1. Provide the maximum number of individuals that

1. May participate in any study interaction or intervention (including screening, consenting, and study activities)

AND/OR

2. You obtain any data/specimens about (regardless of identifiability)

at VCU and at other sites under the VCU IRB's oversight. See the help text for additional guidance.  
200

2. If this is a multi-center project, what is the maximum anticipated number of subjects across all sites?  
NA

3. Provide justification for the sample size by explaining how you arrived at the expected number of participants and why this number is adequate for answering the research questions:  
Power established from a previous pilot study. A previously-approved (institutional review board) pilot study was performed to identify the number of patients needed to obtain sufficient power. Using a reduction in pain score of 50%, alpha of 0.05 and a power of 90%; a sample size of 64 in each group is necessary. The pilot study found that the pain scores were essentially equal by approximately 24 hours, therefore power was calculated for comparison up to about 12 hours postoperatively.

This is also referenced in the research methods section.

The final sample size was determined by the above power analysis and increasing to 200 to account for screen failures.

4. List the study inclusion criteria:

Patients 18 years of age and older, scheduled to undergo a total knee arthroplasty, able to provide informed consent. Patients must receive Duramorph intrathecally.

5. List the study exclusion criteria:

Under the age of 18, using 80 morphine equivalents of narcotic pain medication preoperatively, had a history of allergic reaction to any of the medications used in the study, had creatinine clearance of less than 60 mL/min, currently pregnant, a BMI > 40 and a weight < 75kg. Patients unable to consent in English may be included by using the VCU language services to translate the consent. This population has traditionally been very low in the population that is being offered the study though, so it isn't anticipated to be needed. Patients will not be included if they are allergic to any of the study medications: ropivacaine, clonidine, ketorolac, or epinephrine.

6. Will individuals with limited English proficiency be included in or excluded from this research?

Included

Excluded - safety concerns if participants are unable to communicate with the study team

Excluded - instruments/measures only validated in English

Excluded - no prospect of direct benefit to individual participants

Excluded - minimal risk study

Excluded - lack of budget/resources for translation and interpretation [provide an explanation in next question]

Excluded - other reason [provide an explanation in next question]

7. Justify the inclusion and exclusion criteria if you are either targeting, or excluding, a particular segment of the population / community. Provide a description of the group/organization/community and provide a rationale.

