## Study Procedures

1. **Describe the study hypothesis and/or research questions. Use lay language whenever possible.**  
The study hypothesizes that those receiving intrathecal Duramorph and local periarthicular injections will have reduced narcotic use when compared with intrathecal Duramorph alone at 48 hours postoperatively.

2. **Describe the study's specific aims or goals. Use lay language whenever possible.**  
The study will assess and compare postoperative pain control in patients receiving intrathecal morphine with and without local periarthicular injections.

3. **Choose all types of recruitment materials that may be used and upload them below:**

- E-mail invitations
- Phone Solicitation scripts (i.e. cold calls or random-digit-dialing)
- Flyers, Mailed Letters or Newspaper/TV/Radio Ads
- TelegRAM announcements
- Website text
- Study-specific web sites (provide the design and text)
- Social Media
- EPIC MyChart Patient Portal research study descriptions
- Psychology Research Participant Pool (SONA) study descriptions
- Scripts for announcements made to groups
- Other recruitment material
- No recruitment materials

4. **Describe the study procedures/methods for identifying and recruiting participants. Address the following three aspects of recruitment in your response.**

1. **Identification of potentially eligible participants or secondary data/specimens of interest.**

- What database(s) will be queried to identify secondary data/specimens
- How potential participants' contact information will be obtained

2. **Recruitment procedures to invite participation in the study (when applicable):**

- How each of the written or verbal recruitment materials and reminders (selected above) will be used
- Who will contact or respond to potential participants
- Locations where recruitment procedures will take place
- The timing and frequency of recruitment attempts

3. **Eligibility screening prior to consent and how those activities will be carried out (when applicable)**

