**See the help text for additional guidance**

**Enrollment:**

A previously-approved (institutional review board) pilot study was performed to identify the number of patients needed to obtain sufficient power. Using a reduction in pain score of 50%, alpha of 0.05 and a power of 90%, a sample size of 64 in each group is necessary. The pilot study found that the pain scores were essentially equal by approximately 24 hours, therefore power was calculated for comparison up to about 12 hours postoperatively. 128 patients (64 in each group) undergoing primary total knee arthroplasty by three fellowship-trained orthopedic adult reconstruction surgeons at a single institution will be enrolled into a prospective, double blind, randomized controlled trial.

Patients will be excluded if they are under the age of 18, currently using 80 morphine equivalents of narcotic pain medication daily (pre-operatively), have a history of allergic reaction to any of the medications used in the study, are pregnant, have creatinine clearance of less than 60 mL/min, a BMI > 40 or an actual weight < 75kg.

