## Secondary Data/Specimen Details

1. Describe the source(s) and nature of the information/specimens being obtained. This response should:

- Identify where the data/specimens will come from (e.g., another researcher's registry, pathology lab, commercial source, medical records, etc.); and
- List what types of specimens will be obtained (when applicable); and/or
- List all data elements that will be obtained (when applicable). A data collection form or other documentation may be uploaded and referenced here.

The data being collected includes pain medicine administered for the first 48 hours after surgery. There is a data collection form uploaded in documents. Visual analogue scores are not being collected any longer due to poor reliability.

2. Describe whether any agreement exists between you and data/specimen provider that states you will never have access to the ability to identify the participants (i.e. access to identifiers or the code key) and that you will not attempt to re-identify individuals.

Each subject has a subject number that is being assigned by RedCap (the index number) used as a code. This number is used on the data collection form. Once all data is collected and entered into RedCap this form will be destroyed. Once all data is collected and analyzed all identifiers will be removed from RedCap.

The patient identifiers are in redcap and will not be used in any way that would identify the patient by name. The data will be used in aggregate when reporting the results.

3. When the information/specimens were originally collected, did individuals provide consent for secondary research use of their data/specimens (i.e. consent to another research study or to a research registry)?

Yes

No

HM20004125 [name]  
Do Intraoperative Periarthicular Injections Improve Postoperative Pain Control in Patients Receiving Duramorph? A Prospective, Double  
Blinded, Randomized Controlled Trial

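### The only visible sample-size justification (64 per group, 90% power) is for pain score up to about 12 hours, not for the hypothesised outcome, 48-hour opioid use

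*Combined protocol and SAP*

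**What the plan says.** Study Population, Q3 asks the investigators to explain "why this number is adequate for answering the research questions". The answer is "Using a reduction in pain score of 50%, alpha of 0.05 and a power of 90%; a sample size of 64 in each group". The reason given for the time window is that "The pilot study found that the pain scores were essentially equal by approximately 24 hours", so power was computed for a comparison to about 12 hours. The answer then adds that "The final sample size was determined by the above power analysis", with the rise to 200 covering screen failures only. Study Procedures, Q6 (Enrollment) repeats the same calculation.

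The hypothesis (Study Procedures, Q1) is that patients given intrathecal morphine plus the injection "will have reduced narcotic use when compared with intrathecal Duramorph alone at 48 hours postoperatively".

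On data, Secondary Data/Specimen Details, Q1 says "The data being collected includes pain medicine administered for the first 48 hours after surgery" and "Visual analogue scores are not being collected any longer due to poor reliability". Data and Safety Monitoring, Q8 says that postoperative opioid requirement in morphine equivalents will be assessed. The last free-text answer under Privacy describes the later research activity as chart review of milligrams of pain medicine.

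**The concern.** The powered variable and the hypothesised variable differ in both measure and time: pain score to about 12 hours against opioid use at 48 hours. A reader who takes the Q3 answer at face value will attach 90% power to the opioid comparison, although nothing in the calculation concerns opioids.

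Nor can the pilot effect simply be carried over. The window was cut to 12 hours because the pilot pain difference had gone by about 24 hours, and the hypothesised outcome runs a further day. An early difference in opioid use could persist in a cumulative total, but its size and variance need assumptions of their own.

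What is at stake is interpretation. Without a target difference, a null result on 48-hour opioid use cannot be judged against any effect the trial was designed to find.

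**Working it through.** **1. The plan's own figure.** The inputs stated are a 50% reduction in pain score, alpha 0.05, power 90% and 64 per group. The sidedness, test, SD and control mean are not given, so 64 cannot be derived forward. Solving backwards (normal approximation, two-sided):

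- d = (1.960 + 1.282) × √(2/64) = 0.573
- implied SD/mean of the pain score = 0.5 / 0.573 = 0.87

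So 64 is attainable if the pilot SD was about 0.87 of the control mean, but this cannot be verified. The arithmetic is not the problem.

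**2. What each part of the plan addresses.**

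| Place | Measure | Time |
|---|---|---|
| Study Population, Q3; Enrollment | pain score | to about 12 h |
| Study Procedures, Q1 (hypothesis) | opioid use | 48 h |
| Secondary Data/Specimen Details, Q1 | pain medicine; visual analogue scores dropped | first 48 h |
| Data and Safety Monitoring, Q8 | morphine equivalents | not stated |
| Privacy, last answer | mg of pain medicine | not stated |

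**3. What 64 per group gives for any continuous outcome.** Two-sample t-test (noncentral t), two-sided 0.05, 64 analysed per group:

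- 90% power: d = 0.577; 80% power: d = 0.499
- one-sided 0.05: 0.520 and 0.442
- expected 95% CI half-width: t(0.975, 126) × √(2/64) = 1.979 × 0.1768 = 0.350 SD

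These need no assumption about opioid use, but without an SD and a target difference they do not show that 64 is adequate.

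**4. Illustration for 48-hour opioid use.** The documents give no mean, SD or target. I assume a control-group SD/mean (CV) of 0.6 to 1.0; this has no source in the documents. For a relative reduction r, three models give d:

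- A, equal SDs: d = r / CV
- B, SD proportional to mean: d = r / (CV × √((1 + (1 − r)²)/2))
- C, t-test on the log scale: d = −ln(1 − r) / √(ln(1 + CV²)); this requires that no patient uses zero opioid

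Worked case, r = 0.30 and CV = 0.6: A 0.30/0.6 = 0.500; B 0.30/(0.6 × 0.863) = 0.579; C 0.357/0.555 = 0.643. Power is 80%, 90% and 95%.

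| Reduction | CV | A | B | C |
|---|---|---|---|---|
| 30% | 0.6 | 80% | 90% | 95% |
| 30% | 0.8 | 56% | 68% | 81% |
| 30% | 1.0 | 39% | 50% | 67% |
| 50% | 0.6 | 99.7% | >99.9% | >99.9% |
| 50% | 0.8 | 94% | 99.3% | >99.9% |
| 50% | 1.0 | 80% | 94% | 99.7% |

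Reduction detectable with 90% power at CV 0.6 / 0.8 / 1.0: A 35 / 46 / 58%; B 30 / 38 / 46%; C 27 / 33 / 38%.

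Simulation of the 30% row (40,000 trials per cell) agreed: 80.3 / 90.1 / 95.1% at CV 0.6 and 39.1 / 49.9 / 67.3% at CV 1.0.

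The results fall on both sides of 90%, so the quoted power says nothing either way about the opioid outcome.

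**The case against.** The strongest reply is that the research question is wider than the hypothesis sentence. The title, the aim (Study Procedures, Q2) and the only statement labelled a primary objective (Data and Safety Monitoring, Q8) all speak of postoperative pain control, no primary endpoint is labelled, and a pain score suits that objective. This stands as a limit. It does not close the gap, because the one directional hypothesis is about opioid use and the sentence after the stated objective names opioid requirement.

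Second, that the dropped visual analogue score is the powered pain score is an inference, and nurses still record pain scores hourly (Risks, Q2). Those scores are described as clinical monitoring, and the Privacy section names only milligrams of pain medicine as the later research activity. The inference is reasonable but not certain.

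Third, some text is not visible. The methods description stops at a bare heading for the preoperative intervention, the uploaded data form is not shown, and the list of data is introduced with a word that does not make it exhaustive. A power statement, test or sidedness for opioid use could sit there. Even so, the two places that present the sample size would need to refer to it.

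Fourth, the illustration rests on an unsourced CV and sizes nothing by itself. That is correct; only step 3 is free of assumed inputs. The gap also changes no estimate, test or enrolment target, so one could call it minor. I rate it higher because the plan offers a specific power figure as adequate for a question that the calculation does not cover.

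**Conclusion.** The concern holds and should be fixed. In the visible text, 90% power belongs to a 50% pain-score reduction up to about 12 hours, and not to opioid use at 48 hours. For that outcome the plan shows neither power nor a detectable difference.

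The firm figures, given 64 analysed per group and a two-sided 0.05 t-test, are standardised differences of 0.58 (90% power) and 0.50 (80%), with a CI half-width of 0.35 SD. Under the assumed CV range of 0.6 to 1.0, the reduction detectable with 90% power runs from 27% to 58%, so 64 is neither confirmed nor refuted. The comparison remains unbiased and its type I error is unaffected. Confidence is high for the mismatch in the visible text; it does not extend to what the unseen methods text may contain.

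**What to change.** In Study Population, Q3 and in the Enrollment paragraph, describe the pain-score calculation as the original basis of 64 per group, and make clear that its 90% is not the power for opioid use. Before unblinding, add one sentence of this form:

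*For cumulative 0–48 h morphine equivalents, 64 per group gives [x]% power for a difference of [y] mg, assuming SD [z] mg from [source], by [test and scale], [one/two]-sided alpha 0.05.*

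Take the SD from the pilot if it recorded opioid use, and otherwise from pooled blinded trial data. The pooled SD overstates the within-arm SD by a factor of √(1 + d²/4) under equal SDs: about 4% at d = 0.58, and about 8% at d = 0.83 (a 50% reduction at CV 0.6). The 0.58 and 0.50 figures may be quoted for orientation, but not as the justification. If the unseen methods text already holds such a calculation, cite it in both places instead.

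The cost is one calculation and one paragraph, placed twice, in an amendment. The downside is that the restated power may be below 90%. No increase in enrolment is implied.

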## Study Procedures

1. **Describe the study hypothesis and/or research questions. Use lay language whenever possible.**  
The study hypothesizes that those receiving intrathecal Duramorph and local periarthicular injections will have reduced narcotic use when compared with intrathecal Duramorph alone at 48 hours postoperatively.

2. **Describe the study's specific aims or goals. Use lay language whenever possible.**  
The study will assess and compare postoperative pain control in patients receiving intrathecal morphine with and without local periarthicular injections.

3. **Choose all types of recruitment materials that may be used and upload them below:**

- E-mail invitations
- Phone Solicitation scripts (i.e. cold calls or random-digit-dialing)
- Flyers, Mailed Letters or Newspaper/TV/Radio Ads
- TelegRAM announcements
- Website text
- Study-specific web sites (provide the design and text)
- Social Media
- EPIC MyChart Patient Portal research study descriptions
- Psychology Research Participant Pool (SONA) study descriptions
- Scripts for announcements made to groups
- Other recruitment material
- No recruitment materials

4. **Describe the study procedures/methods for identifying and recruiting participants. Address the following three aspects of recruitment in your response.**

1. **Identification of potentially eligible participants or secondary data/specimens of interest.**

- What database(s) will be queried to identify secondary data/specimens
- How potential participants' contact information will be obtained

2. **Recruitment procedures to invite participation in the study (when applicable):**

- How each of the written or verbal recruitment materials and reminders (selected above) will be used
- Who will contact or respond to potential participants
- Locations where recruitment procedures will take place
- The timing and frequency of recruitment attempts

3. **Eligibility screening prior to consent and how those activities will be carried out (when applicable)**

**See the help text for additional guidance.**

Patients will be recruited at either the NOW center (Short Pump), Stony Point Outpatient Clinic or the Ambulatory Care Center clinics. Patients will be informed of the study once he/she has elected to undergo a total knee arthroplasty and has signed a consent for that procedure. If interested in joining the study, they will be given an informed consent to review and sign. The study will only be offered to those patients that have already signed a consent for the knee arthroplasty procedure.

The attending physicians who have made the decision that a TKR is medically necessary will determine if a patient is eligible.

The Orthopedic department has multiple studies being done in patients undergoing a TKR. Some of the studies have priority over others. Once it has been determined which studies a patient is being offered, they will be given a consent and it will be reviewed by the current orthopedic fellow. In the interest of improving our subject recruitment, some patients may be called via telephone to discuss the study. (see attached script). The actual consent will be reviewed and signed prior to surgery in the perioperative area where the patient will also have the opportunity to ask any further questions.

The fellow may also review the study to all eligible patients at their medical appointments (these occur approximately one month prior to surgery). As noted previously, they will be given this information in a private examination room and given time to ask questions and/or to take the ICF home and peruse it. Any questions can be directed to the fellow. This is all done once the decision has been made to perform a TKR.

5. **Does this study have a separate protocol document (i.e. a multisite or sponsor's protocol) that contains a detailed description of the study's methodology?**

- Yes
- No

6. **Since a separate protocol document is not uploaded, describe the proposed research using language understandable to those IRB committee members whose expertise is not scientific. The description must include:**

1. A statement explaining the study design
2. A detailed description of all the procedures that will be followed to carry out the study, preferably in sequential order, and in sufficient detail that the study's methods could be replicated
3. A description of all research measures/tests/interventions that will be used (if applicable)

**See the help text for additional guidance**

**Enrollment:**

A previously-approved (institutional review board) pilot study was performed to identify the number of patients needed to obtain sufficient power. Using a reduction in pain score of 50%, alpha of 0.05 and a power of 90%, a sample size of 64 in each group is necessary. The pilot study found that the pain scores were essentially equal by approximately 24 hours, therefore power was calculated for comparison up to about 12 hours postoperatively. 128 patients (64 in each group) undergoing primary total knee arthroplasty by three fellowship-trained orthopedic adult reconstruction surgeons at a single institution will be enrolled into a prospective, double blind, randomized controlled trial.

Patients will be excluded if they are under the age of 18, currently using 80 morphine equivalents of narcotic pain medication daily (pre-operatively), have a history of allergic reaction to any of the medications used in the study, are pregnant, have creatinine clearance of less than 60 mL/min, a BMI > 40 or an actual weight < 75kg.

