A full review of the patient's medical record, including allergies, will be performed to minimize allergic and other adverse drug reactions. The periarthicular injection will be placed in a region away from nerves so as to prevent temporary or permanent weakness/numbness.

In patients who do not receive the periarthicular injection, they will continue to receive other important components of the perioperative multimodal analgesia protocol.

Patients are monitored at least daily by medical staff after undergoing TKR. Nursing protocol monitors pain scores and pain acceptance rates on an hourly basis post-surgically. Any side effects will be noted during this monitoring process. As previously noted, the risks in this study are notably, potential pain by not receiving the per-articular joint injection, since all patients who are NOT enrolled in the study will likely receive the injection.

3. Describe any potential risks or harms to a community or a specific population based on study findings (e.g. information that could be stigmatizing or derogatory):

None

4. Where appropriate, discuss provisions for ensuring necessary medical, professional, or psychological intervention in the event of adverse events to the subjects:

If there is any adverse reaction to the injection this will be handled by the orthopedic physicians who are caring for the patient during their surgery.

5. Describe criteria for when the investigator would withdraw an individual participant from the study; such as safety or toxicity concerns, emotional distress, inability to comply with the protocol, etc.:

If there is a toxicity or adverse reaction concern, the patient will be withdrawn from data collection and treated appropriately according to current medical guidelines and standards.

Any toxicity event or adverse effects will be managed with the use of fluids, and medications such as anti-emetics. Patient level of monitoring may be increased to allow for closer observation and treatment. Other treatment interventions will be managed with additional interventions as deemed necessary by the treating physicians.

6. Summarize any pre-specified criteria that would trigger the investigator/sponsor/monitoring committee to stop or change the study protocol due to safety concerns:

NA

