### Data and Safety Monitoring

Data and safety monitoring is a system for checking the study's data at regular intervals over the study period to identify and address issues that could affect the safety of research participants. This requirement is in accordance with 45 CFR 46.111.

The purpose of data and safety monitoring plan is to set forth study team procedures for monitoring/addressing:

- Participant safety (physioal, psychological, etc.)
- Data validity
- Early stopping (termination) based upon changes in risks and benefits.

7. Indicate if this study will have a Data Safety Monitoring Board (DSMB) or a Data Safety Monitoring Plan (DSMP): (Required for all greater than minimal risk studies)

- DSMB
- DSMP
- No DSMB/DSMP (Note: This response is not applicable for greater than minimal risk studies)

8. Describe your Data Safety Monitoring Plan for monitoring the study's data to ensure the safety of participants. This plan should include (but is not limited to) the following elements:

1. Who will monitor data
2. What data and/or processes will be reviewed
3. When and how frequently monitoring will occur
4. What report/documentation will be submitted to the IRB at the time of continuing reviews

See the help text for additional guidance.

The primary objective is to assess and compare postoperative pain control in patients receiving intrathecal morphine with and without a local periarthicular injection.

Opiate requirements postoperatively (morphine equivalents) will be assessed.

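### Does the comparison of 48-hour opioid use need to record and adjust for pre-operative opioid dose?

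*Combined protocol and SAP*

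**What the plan says.** Opioid use before surgery appears only as an exclusion. Study Population, question 5, excludes patients "using 80 morphine equivalents of narcotic pain medication preoperatively". The Enrollment text under Study Procedures adds that the amount is per day: "currently using 80 morphine equivalents of narcotic pain medication daily (pre-operatively". Read as a limit, both leave patients on smaller amounts eligible.

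The hypothesis in Study Procedures, question 1, is that the injected group "will have reduced narcotic use when compared with intrathecal Duramorph alone at 48 hours postoperatively". Data and Safety Monitoring gives the measure: "Opiate requirements postoperatively (morphine equivalents) will be assessed".

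On data items, Secondary Data/Specimen Details, question 1, says: "The data being collected includes pain medicine administered for the first 48 hours after surgery". It then adds: "There is a data collection form uploaded in documents". That form is not among the pages available.

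The Data Analysis Plans section deals with interim analysis, adverse-event review and stopping rules. It names no test, model or covariate. The Randomization text describes a pharmacy schedule and mentions no stratification. The methods narrative breaks off at the heading Preoperative Intervention, with nothing readable beneath it.

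**The concern.** A patient who takes opioids before surgery may well need more of them afterwards. If so, pre-operative dose explains part of the spread in the 48-hour total, and a model that includes it gives a narrower interval for the treatment difference. Nothing in the readable text uses this baseline: it is not a stratification factor, a listed data item or a covariate.

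A possible loss of precision deserves a look here because 64 per group was set from pain scores up to about 12 hours. Visual analogue scores are no longer collected, so the documents give no power figure for the 48-hour opioid outcome. Adjustment would not repair that mismatch, which is a separate matter.

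Recording the item also looks cheap. Eligibility already requires a check of pre-operative opioid use, and the risk section plans a review of the "medical record, including allergies, will be performed to minimize allergic and other adverse drug reactions". The possible gain would be lost if the value were never recorded and the link to the chart were then destroyed.

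**Working it through.** **1. The plan's own figure.** The Enrollment text gives 64 per group for a 50% fall in pain score, alpha 0.05 and 90% power. It gives no SD, control mean or sidedness, so 64 can only be solved backwards. With a two-sided t-test, 64 per group has 90% power at a standardised difference of 0.577. It has 80.1% power at 0.5. Both values are used below as illustrations on the opioid scale; neither comes from opioid data.

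**2. Inputs for the adjusted analysis.**
- From the plan: 64 per group (N = 128) and alpha 0.05.
- Assumed: a two-sided test; two baseline terms (any use, and dose); a multiple correlation r between those terms and the outcome; and the difference d in SD units.

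**3. Formula.** With k = 2 covariates, the variance of the treatment difference is multiplied by

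(1 − r²) × (1 + k/(N − k − 3)) = (1 − r²) × (1 + 2/123).

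The second factor is the average cost of chance imbalance in the covariates. Error degrees of freedom fall from 126 to 124. Power comes from the noncentral t distribution with noncentrality d × √(64/2) ÷ √(variance factor). The unadjusted value at d = 0.5 is 0.5 × √32 = 2.828, which gives 80.1%.

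**4. Results.**

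| r | Power, d = 0.5 (unadjusted 80.1%) | Power, d = 0.577 (unadjusted 90.0%) | Change in 95% CI width |
|---|---|---|---|
| 0 | 79.5% | 89.5% | +0.8% |
| 0.1 | 79.9% | 89.8% | +0.3% |
| 0.2 | 81.1% | 90.7% | −1.2% |
| 0.3 | 83.1% | 92.1% | −3.8% |
| 0.4 | 85.9% | 93.9% | −7.6% |
| 0.5 | 89.5% | 96.0% | −12.7% |

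Break-even is at r = 0.127. At d = 0.5, a gain of 2 points needs r of about 0.26, and a gain of 5 points needs about 0.37.

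**5. What r might be.** Suppose a share p of patients use opioids before surgery and need D SDs more afterwards than non-users. Then r² = p(1 − p)D² ÷ (1 + p(1 − p)D²). This treats use as yes/no only; a dose term could raise r.

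| p | D | p(1 − p)D² | r | Against break-even (0.127) |
|---|---|---|---|---|
| 10% | 0.25 | 0.0056 | 0.07 | below: small loss |
| 5% | 0.5 | 0.0119 | 0.11 | below: small loss |
| 10% | 0.5 | 0.0225 | 0.15 | just above |
| 20% | 1.0 | 0.1600 | 0.37 | gain of about 5 points at d = 0.5 |
| 30% | 1.5 | 0.4725 | 0.57 | larger gain |

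The documents give neither p nor D, so they cannot say which row applies.

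**6. Bias.** Pre-operative dose is fixed before randomisation. Any difference between groups on it is due to chance, and the unadjusted interval already allows for that. Nothing in steps 3 to 5 affects the validity of the unadjusted comparison.

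**The case for a change.** The best argument for acting is that the stakes are lopsided. At d = 0.5 the worst outcome is a loss of about 0.6 points of power; at r = 0.4 the gain is 5.8 points and the interval is 7.6% narrower. Against that stand one chart field and a few sentences, written before unblinding so that the model is not chosen from the data. Timing adds some weight, since a baseline never recorded cannot be recovered once the linking key is gone.

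The arithmetic stands, and so does the point about fixing the model before unblinding. The rest is weaker:

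- **Absence is not shown.** The list of data items is worded as inclusive and points to a form that cannot be seen, and the methods text is cut off. Either may already record pre-operative dose or name the analysis.
- **The cost is more than one field.** Checking a threshold does not require writing down a number. The planned record review is aimed at adverse drug reactions, not at measuring home opioid use. Data collection also appears to be under way, so a new item could mean returning to the charts of patients already enrolled.
- **The model is open to debate.** Whether to transform the outcome, which baseline terms to use and whether to add other covariates are choices on which competent statisticians differ. Nothing in the documents settles them.
- **Key timing is a separate matter.** Secondary Data/Specimen Details says "Once all data is collected and analyzed all identifiers will be removed from RedCap", whereas the privacy and confidentiality sections tie de-identification and destruction of the key to the end of data collection. That is a point of data governance and alters no result.

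**Conclusion.** No change to the plan is called for. The observation is accurate for the text that can be read: patients on lower pre-operative doses appear eligible, and neither their dose nor an adjusted model is named. But the unadjusted comparison answers the trial's question without bias, and adjustment is an optional gain in precision of unknown size. With 64 per group and a true difference of 0.5 SD, the change in power runs from −0.6 points at r = 0 to +5.8 points at r = 0.4 and +9.4 at r = 0.5. It is within about 1 point either way for r up to 0.2.

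These figures rest on assumed values of r and d, a two-sided test and a linear model with two baseline terms. If pre-operative use proves common and strongly related to later need, the statistician can sensibly add the covariate when writing the analysis, before unblinding. If it proves rare, adjustment gains nothing.
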